Nevertheless, the effectiveness and tolerability of finerenone in patients with non-diabetic chronic kidney disease (CKD) have not yet been clearly established [25]. The design of this study aims to determine whether the renal protective benefits of finerenone also apply to non-diabetic CKD patients, including those with an estimated glomerular filtration rate (eGFR) below 15 ml/min/1.73m² [26]. To our knowledge, our investigation is pioneering in assessing the therapeutic potential and safety profile of finerenone for this specific patient group [27].

II. Research Objective

To assess the progression of kidney disease in non-diabetic CKD patients following the use of finerenone, and to analyze the safety profile of finerenone.

III. Research Content

Investigate the changes in renal function in non-diabetic CKD patients after the administration of finerenone.

Analyze the relationship between the use of finerenone and cardiovascular events.

Evaluate the safety of finerenone treatment.

IV. Research Methodology

(A) Study Design

This project is a single-center, retrospective cohort study.

(B) Study Population

The study population comprises patients who were hospitalized for treatment or followed up on an outpatient basis in the Department of Nephrology, the First Hospital affiliated with Harbin Medical University, starting from December 15, 2023. The baseline for the study is defined as the occasion when a patient with CKD (either as a primary or secondary diagnosis) was first admitted to the nephrology department for hospital treatment or an outpatient visit.

Inclusion criteria:

- (1) Patients who were hospitalized or followed up on an outpatient basis in the Department of Nephrology, the First Hospital affiliated with Harbin Medical University, starting from December 15, 2023;
- (2) Patients with non-diabetic kidney disease;
- (3) Patients with electronic medical records available.

Exclusion criteria:

- (1) Type 2 diabetes mellitus;

(2) Patients who refuse to participate.

(C) Study Variables

In accordance with the research objectives, the project will collect the following variables:

Baseline patient characteristics: including age, gender, stage of kidney disease, comorbidities, medication history, etc.

Use of finerenone: including dosage, duration of therapy, etc.

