Kidney-related indicators and cardiovascular events: including eGFR, serum creatinine levels, records of kidney disease events (such as renal function decline, initiation of dialysis, or kidney transplantation), and records of cardiovascular events.

Safety data: including all adverse events recorded.

(D) Data Collection and Data Management

Determine data sources:

The data will primarily be sourced from the hospital's electronic health record HIS system, which may include clinical records, medication administration records, laboratory test results, and radiological reports.

Acquisition of patient information:

Based on the study's inclusion and exclusion criteria, construct a query to compile a list of patients from the hospital database who meet the criteria for CKD.

Creation of data collection forms:

Create a standardized data collection form listing all the information that needs to be gathered.

Ensure the form includes all the key variable items involved in the study.

Data extraction:

Use the search and export functions of the EHR system to export the required data points for each patient involved in the study. This includes the patient's basic information, medication usage, laboratory test results, etc. For information that cannot be collected automatically, such as physicians' notes or qualitative descriptions in radiological reports, manually extract or enter these into the data tables.

Data entry and coding:

Enter the extracted data into the data collection forms. To protect patient privacy, encode patient information wherever possible to anonymize patient identity within the dataset. For qualitative data, such as diagnoses or symptom descriptions, develop a standardized coding system that converts them into quantitative data suitable for statistical analysis.

Quality control:

Perform data cleaning on the preliminary collected data, checking for missing data, outliers, and inconsistencies. Conduct data verification to ensure the accuracy and completeness of all data. If possible, have two research assistants perform data extraction and entry independently and reconcile any discrepancies.

Data storage and security:

Ensure that all electronic data is stored on secure, password-protected servers or cloud services. Regularly back up data to mitigate the risk of data loss.

Ethical compliance:

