Ensure that all data collection and processing adhere to the ethical guidelines of the hospital and research institution, local medical regulations, and data privacy laws. If direct communication

with patients is necessary to collect data, obtain informed consent from the patient.

V. Statistical Analysis

In a single-center retrospective study, the data analysis process is complex and multi-step, aimed at extracting meaningful conclusions and insights. Below is a detailed description of the data analysis:

Data cleaning:

Prior to formal analysis, data cleaning is conducted to remove incomplete, incorrect, or inconsistent records.

Missing data are appropriately addressed, for example through imputation or deletion of missing entries.

Duplicate records are checked and resolved to ensure the uniqueness of analysis.

Descriptive statistical analysis:

Descriptive statistical analysis is performed on basic patient characteristics, including age, gender, stage of CKD, etc.

Medication usage of finerenone is quantified (dose, duration of treatment, etc.).

Primary and secondary outcome measures are descriptively analyzed (e.g., changes in renal function, incidence of cardiovascular events).

Exploratory Data Analysis (EDA):

Data within the set is visualized using bar charts, box plots, scatter plots, and other visualization tools to explore potential patterns or trends.

Variables potentially affecting study outcomes are extracted for exploration of relationships between variables.

Hypothesis testing:

If the study aims to compare renal function before and after treatment with finerenone, hypothesis testing might be conducted using parametric or nonparametric methods such as paired sample t-tests or Wilcoxon signed-rank tests.

In the presence of multiple groups (e.g., patients with different stages of CKD), methods such as ANOVA or Kruskal-Wallis may be used to compare differences between groups.

Regression analysis:

Linear regression analysis is conducted to assess the degree of association between continuous variables.

Binary logistic regression analysis is utilized for non-continuous outcome variables, such as the occurrence of cardiovascular events.

Multivariate regression analysis may be applied, if appropriate, to adjust for potential confounding factors.

Survival analysis:

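### Logistic regression, with no person-time term or fixed risk window, is the only inferential method named for cardiovascular events; unequal follow-up can bias the finerenone odds ratio

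*Combined protocol and SAP*

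**What the plan says.** Section III makes the cardiovascular question one of three research contents: "Analyze the relationship between the use of finerenone and cardiovascular events".

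Section V, Regression analysis, assigns the method: "Binary logistic regression analysis is utilized for non-continuous outcome variables, such as the occurrence of cardiovascular events". Section V names these events in one other place, the descriptive analysis, where their incidence is listed without a definition as a rate or a time window.

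Section V, Survival analysis, offers Kaplan-Meier curves, log-rank tests and a Cox model. All are conditional on follow-up data being analysed and are worded as possibilities. The example given is progression of kidney disease. The Cox sentence refers to treatment and outcomes in general and states no time origin or exposure coding.

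Section IV (B) admits "Patients who were hospitalized or followed up on an outpatient basis in the Department of Nephrology" at "the First Hospital affiliated with Harbin Medical University, starting from December 15, 2023". It gives no end date, follow-up length or censoring rule. Baseline is the occasion when the patient "was first admitted to the nephrology department for hospital treatment or an outpatient visit". It defines no comparator; a control group appears only in the log-rank sentence.

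Section IV (C) lists "Use of finerenone: including dosage, duration of therapy, etc" and "records of cardiovascular events". Neither item names dates, and no rule for coding exposure is given.

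**The concern.** A logistic model of whether an event occurred treats a patient observed for 9 months and one observed for 18 months as equally informative. Open entry with no common closing rule makes unequal observation likely. If its length is related to finerenone use, a drug with no effect can look protective or harmful. The same problem arises without a control group if duration of therapy is the exposure among users: longer observation allows both more treatment and more events.

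The second issue is timing. Because baseline is the first visit, some patients may start finerenone later. If they are coded as ever or never users, the result depends on how events before the first dose are handled, and the plan is silent on this.

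**Working it through.** **Inputs.** The plan gives no event rate, follow-up length, effect size or planned sample size, so there is no figure of its own to reproduce. Everything below is illustrative. Assumptions: no drug effect and a constant rate λ of 0.05 or 0.10 events per patient-year, except in step 3. The only number taken from the plan is the 43 cases in section VIII.

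**1. Unequal follow-up, exposure fixed at baseline.** Risk = 1 − exp(−λt), and OR is the ratio of the odds.

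- λ = 0.05, 15 v 12 months: risks 0.0606 v 0.0488, OR 1.258; reversed, 0.795.
- λ = 0.10, 15 v 12 months: risks 0.1175 v 0.0952, OR 1.266; reversed, 0.790.
- A smaller gap, 13.2 v 12 months: OR 1.103 and 1.106.
- Equal follow-up: OR 1.00.

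**2. Ever/never coding from the first visit, everyone followed for 12 months.** A share f = 0.5 is due to start at a time uniform over 0 to L = 0.5 years. The probability of being event-free at the planned start is m = (1 − exp(−λL))/(λL), which is 0.9876 for λ = 0.05 and 0.9754 for λ = 0.10. Three counting rules are possible.

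- *An event prevents starting.* Exposed risk = (m − exp(−λ))/m = 0.0368 and 0.0724. Unexposed risk = [(1 − f)(1 − exp(−λ)) + f(1 − m)]/[(1 − f) + f(1 − m)] = 0.0604 and 0.1169. OR = 0.595 and 0.589.
- *All who are due start, but only first events after the first dose count for the exposed.* Exposed risk = m − exp(−λ) = 0.0364 and 0.0706, against 0.0488 and 0.0952. OR = 0.736 and 0.722.
- *Patients may start after a non-fatal event, starting is unaffected by it, and all events count.* Both groups have risk 0.0488 (or 0.0952), so OR = 1.00. Events before the first dose are then attributed to the drug.

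Under the first rule, starts spread over months 0–3 give OR 0.77 and over months 0–1 give 0.92. If all start at the baseline visit, the bias is zero.

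**3. Does person-time cure it?** Under the first rule with starts over months 0–6, a person-time rate ratio with ever/never coding is still 0.59 to 0.60. Splitting time at the first dose gives 1.00, so the exposure rule matters as much as the model.

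That 1.00 rests on a constant rate. Baseline can be a hospital admission, so early risk may be higher, and unexposed time falls early. Take the same start pattern with an assumed rate 2 or 4 times higher in months 0–3, no drug effect, and Poisson regression with time-varying exposure and only a log person-time offset. For a later rate of 0.05, expected values per patient are:

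- 2 times: exposed 0.01950 events in 0.3594 years; unexposed 0.04108 in 0.6055 years. Rate ratio 0.0543/0.0678 = 0.80.
- 4 times: exposed 0.02207 in 0.3507 years; unexposed 0.06171 in 0.5933 years. Rate ratio 0.0629/0.1040 = 0.61 (0.60 for a later rate of 0.10).

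Stratifying on time since baseline restores 0.99 to 1.00. A Cox model on that time scale does this by design.

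**4. Precision.** For 43 cases with an assumed 9 to 18 months each, expected events run from 43 × (1 − exp(−0.05 × 0.75)) = 1.6 to 43 × (1 − exp(−0.10 × 1.5)) = 6.0. A split of 3 v 3 events in equal person-time gives an exact 95% interval for the rate ratio of 0.13 to 7.47.

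**The case against.** The strongest reply is that the plan already contains suitable tools. The Cox sentence speaks of treatment and outcomes with adjustment for confounders, which fits the cardiovascular aim, and kidney disease progression is only an example there. This stands in part: time-to-event analysis is not excluded. But it is optional, whereas the logistic line is stated as what will be done. Nor does listing Cox settle the time origin or the exposure coding.

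A reader might infer that time before the first dose is event-free by construction for every ever-user, so that the odds ratio must favour finerenone. The documents do not support this. It is true of death, but a patient can have a non-fatal event and start the drug afterwards. Bias from ever/never coding needs a further rule, and the plan states neither that rule nor ever/never coding itself.

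It is also fair to say that no comparator is defined. Without a contrast in finerenone use, whether between users and non-users or by duration among users, there is no odds ratio to bias. The aim of relating use to events nevertheless requires some contrast.

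Finally, the variable lists are open-ended, and duration of therapy is normally derived from start and stop dates. Dates may well be collected; they are just not named.

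**Conclusion.** The point holds in a limited form. The plan commits cardiovascular events to logistic regression without person-time or a fixed window, and leaves the methods that handle unequal follow-up optional. If that line is followed and follow-up differs by exposure, the odds ratio is biased in either direction: about 1.26 to 1.27, or 0.790 to 0.795, for a three-month difference under the stated assumptions. Ever/never coding could add a bias to about 0.59 or to 0.72–0.74, or none at all, depending on an unstated rule.

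The documents give no follow-up by exposure and no timing of starts, so they do not show that the study's result is biased, or in which direction. At the 43 cases organized so far, which is not a planned size, random error is far larger than these biases. Priority is modest and rises if the cohort grows.

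**What to change.** In section V, Regression analysis, replace logistic regression for cardiovascular events with the following.

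- **Model.** Cox regression on time since baseline, with finerenone as a time-varying exposure: time and events before the first dose count as unexposed. State in advance how time after stopping is counted.
- **Follow-up.** Start at baseline, with delayed entry if the first visit preceded 15 December 2023. End at the first event, death, last contact or a stated cut-off date.
- **Alternative.** If Poisson regression with a log person-time offset is preferred, include time since baseline in the model.
- **Few events.** If there are too few for a model, report events, person-years and rates with exact intervals by exposure.
- **Logistic regression.** Keep it only for a fixed window fully observed for every included patient, with exposure fixed at the start of that window.
- **Comparator.** Define it in section IV (B). If there is none, report the event rate descriptively.
- **Data.** Put event dates, finerenone start and stop dates, and last-contact dates explicitly on the data collection form.

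The cost is rewording and some manual date extraction, with no extra patients. The sources in section IV (D), "which may include clinical records, medication administration records, laboratory test results, and radiological reports", should hold most of the dates. Estimates will remain imprecise at the present number of cases under any model.

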If the study includes analysis of follow-up data, such as tracking the progression of CKD, Kaplan-Meier survival curves can be used for description, and Log-rank tests to assess differences between treatment and control groups.

Cox proportional hazards model could be employed to determine the relationship between

treatment and outcomes while adjusting for confounders.

Use of statistical software:

Complex statistical analyses are performed using statistical software packages such as SPSS, Stata, R, or Python.

Data integrity is maintained throughout the analysis, and all analysis steps are documented for later review.

Interpretation of results:

Attention is given to the levels of statistical significance, and methods like Bonferroni correction are applied to address issues of multiple comparisons.

Statistical findings are translated into clinically meaningful narratives that can be understood and used by physicians or researchers.

Discussion and comparison:

Results are compared with existing literature and other studies to discuss possible reasons for any discrepancies.

Limitations of the study findings are highlighted, and areas needing further research are proposed.

Report writing:

Based on the results of the analysis, a research report or scientific paper is composed, including the methods, data analysis process, results, conclusions, and recommendations.

Through these steps, researchers can effectively draw conclusions from large data sets and provide evidence for clinical decision-making or further research. Throughout all these stages, adherence to statistical principles, data privacy regulations, and ethical guidelines is crucial.

VI. Ethics

Ethical Committee Review

The research protocol, informed consent forms, and any materials directly related to the patients must be submitted to the ethics committee for written approval before the research can formally commence. The ethics committee must be notified in writing upon cessation and/or completion of the study. Researchers are required to promptly report any changes occurring in the research work to the ethics committee (such as revisions to the research protocol and/or informed consent forms) and must not implement these changes prior to obtaining the committee's approval, unless the changes are made to eliminate apparent and direct risks to the enrolled patients.

Informed Consent

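### No adjusted analysis is fixed as the main finerenone-versus-control comparison; controls are undefined and baseline is not tied to the start of treatment, so a null drug could look protective or harmful

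*Combined protocol and SAP*

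**What the plan says.** Section IV(A) states the design: "This project is a single-center, retrospective cohort study". Finerenone is not allocated; section IV(C) records it as an exposure, "Use of finerenone: including dosage, duration of therapy, etc".

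The inclusion criteria in section IV(B) ask for "Patients with non-diabetic kidney disease" and do not mention use or non-use of finerenone. No rule separates users from non-users. Time zero is set by a visit: "The baseline for the study is defined as the occasion when a patient with CKD" was first admitted to, or seen as an outpatient in, the nephrology department.

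Section V, Survival analysis, opens with a condition, "If the study includes analysis of follow-up data, such as tracking the progression of CKD, Kaplan-Meier survival curves can be used for description", and then names "Log-rank tests to assess differences between treatment and control groups". This is the only place where a control group is mentioned. The next sentence offers adjustment: "Cox proportional hazards model could be employed to determine the relationship between" treatment and outcomes, with confounders adjusted for. Under Regression analysis, linear and logistic models are listed, followed by "Multivariate regression analysis may be applied, if appropriate, to adjust for potential confounding factors". No covariate is assigned to any model, and no matching, weighting or propensity score is named.

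Under Hypothesis testing, a within-patient before-after comparison of renal function is another possibility, also conditional.

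**The concern.** Clinicians chose who received finerenone. Users and non-users may differ in kidney function, co-medication, cardiovascular history, and whether they entered as inpatients or outpatients. A crude comparison mixes those differences with any effect of the drug, and the mixture does not shrink as the sample grows. More patients only make the wrong answer look more certain.

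The plan recognises confounding but does not commit to dealing with it. Crude and adjusted results are both permitted, nobody is told which is the main one, and the covariates are open. Section VIII says that 43 cases have already been examined with significant differences, so these choices could now be made with results in view.

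Time zero is a separate problem. If follow-up starts at the first visit and a patient who starts finerenone later is counted as treated from that visit, the patient cannot have had the event between visit and start. That event-free time is credited to the drug.

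The association between finerenone and cardiovascular events is a stated research item (section III), and section V expects the results to inform clinical decisions.

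**Working it through.** The documents give no sample size, power, alpha, event rate or effect size, so there is no figure of the plan's own to reproduce. What follows is illustration. Every input is an assumption unless marked otherwise. The drug has no effect throughout, and tests are two-sided at 5%.

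**1. Size of the confounding bias.** Let one binary risk factor with hazard ratio H be present in a share p1 of users and p0 of non-users. At the start of follow-up, the crude hazard ratio is

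(1 + p1(H − 1)) / (1 + p0(H − 1)).

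- 40% vs 70%, H = 3: 1.8 / 2.4 = 0.75.
- 70% vs 40%, H = 3: 2.4 / 1.8 = 1.33 (simulated rate ratio about 1.35).
- Mild, 40% vs 60%, H = 2: 1.4 / 1.6 = 0.875.

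**2. False-positive rate of the unadjusted log-rank.** Simulated with a base hazard of 12% per year and follow-up of 0.5 to 2.5 years. The group size of 43 borrows the case count in section VIII, which gives no split between users and controls.

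- 40% vs 70%, H = 3: about 12% (43 vs 43), 13% (43 vs 150) and 20% (100 vs 100). Repeat runs agreed within about two percentage points. At 200 vs 200 the rate was 37%.
- 70% vs 40%, H = 3, 43 vs 43: about 12%, with only 0.3% in the protective direction.
- Mild, 40% vs 60%, H = 2: about 6%.

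**3. A second set of assumptions.** One year of follow-up, 20% one-year risk in low-risk patients, equal groups. N is the total.

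| High-risk share, users vs controls | H | Crude rate ratio | N = 43 | N = 200 | N = 400 |
|---|---|---|---|---|---|
| 40% vs 40% | 3 | 1.00 | 5.2% | 5.1% | 4.8% |
| 30% vs 50% | 2 | 0.87 | 5.2% | 8.9% | 11.1% |
| 30% vs 50% | 3 | 0.80 | 6.8% | 14.2% | 22.9% |
| 50% vs 30% | 3 | 1.25 | 7.0% | 14.8% | 24.1% |
| 20% vs 60% | 4 | 0.57 | 19.0% | 65.6% | 91.2% |

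**4. After adjustment.** Stratifying the log-rank by the same factor brought the false-positive rate to 4.6–5.7% in every setting of step 3. This holds for a measured confounder only.

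**5. Time zero.** Now assume no confounding, 20% one-year risk for everyone, about half of patients intended for the drug, starts spread evenly after the first visit, and ever-users counted as treated from that visit.

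- Starts over 3 months: rate ratio about 0.77; falsely significant in 6.6% (N = 43) and 13.0% (N = 200).
- Over 6 months: about 0.59; 9.9% and 37.8%.
- Over 12 months: about 0.34; 28.3% and 89.1%.

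The adjustment in step 4 does not cure this. It needs an aligned index date.

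**The case against.** The strongest reply is that section V is a menu. The log-rank is conditional, the sentence after it offers a Cox model with adjustment for confounders, and the regression paragraph mentions confounding too. A reader might infer that the plan commits to testing finerenone by a crude log-rank, or that it ignores confounding. The documents support neither. What stands is narrower: nothing requires the adjusted analysis or makes it the main one.

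Second, user against non-user may not be the main question. The objective and the renal item speak of change following the drug, and a paired test is listed. That is fair for the renal outcome. The cardiovascular item, however, concerns a relationship with use of the drug and implies a comparator, and section V itself refers to a control group.

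Third, a reader might infer that the plan will favour the drug. The documents do not show who was prescribed it. The introduction includes patients with eGFR below 15, so users could be the sicker group and a null drug could look harmful. Only the time-zero problem has a clear direction, and only if ever-users are counted as treated from the first visit, which the plan does not say.

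Fourth, it is tempting to call the significant differences in the first 43 cases an artefact. The documents do not say what was compared, so that cannot be concluded.

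Finally, the sizes come from chosen inputs, and under mild imbalance the test is close to nominal. That stands.

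**Conclusion.** The concern holds as a failure to commit. In a non-randomised cohort, the plan fixes no adjusted main comparison, no covariate set, no control group and no index date tied to treatment. A fully compliant analysis could therefore be confounded in either direction.

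The size is conditional: from almost nothing under mild imbalance to several times the nominal error rate under strong imbalance or larger samples. The illustrations assume a single binary confounder, a null drug and two-sided 5% testing. They show what the wording permits, not what the data contain. The change should be made before further analysis.

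**What to change.** For any comparison of users with non-users, on progression or on cardiovascular events:

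1. In section IV(B), define users from the start of finerenone and controls as eligible patients not on finerenone at a matched index date. Take covariates and follow-up from that date for both groups.
2. In section V, name one adjusted analysis as the main result, for example: *The main comparison will be a Cox model weighted by propensity-score overlap weights.* Other adjusted methods would serve, but one must be chosen in advance.
3. Fix a short covariate set from information already collected: age, sex, eGFR or CKD stage, cardiovascular history, ACE inhibitor or ARB use, SGLT2 inhibitor use, and inpatient or outpatient entry. Size it to the data. Under the assumptions of step 2, 43 vs 43 yields about 25 events, so seven covariates in an ordinary Cox model would leave 25 / 7 ≈ 3.6 events each. Add proteinuria and blood pressure if they can be extracted; neither is a listed variable.
4. Replace the permissive wording for regression and Cox adjustment with a firm commitment for these comparisons, and keep the log-rank as crude description.
5. State that the before-after renal analysis has no control and will not on its own be read as a drug effect. The steps above do not repair it.

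The cost is some extra data extraction and programming, wider intervals, and possibly a less favourable result. Unmeasured confounding remains and should be stated as a limitation.

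### Kaplan-Meier is offered for CKD progression with no rule for death and no all-cause death variable; if deaths are censored, the absolute risk of progression is overstated

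*Combined protocol and SAP*

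**What the plan says.** Section V (Survival analysis) is conditional. It opens "If the study includes analysis of follow-up data, such as tracking the progression of CKD" and then says that "Kaplan-Meier survival curves can be used for description", followed by "Log-rank tests to assess differences between treatment and control groups". For adjustment, a "Cox proportional hazards model could be employed to determine the relationship between" treatment and outcomes. The section defines no time-to-event endpoint, time origin or censoring rule, and it does not say what happens to a patient who dies.

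Section IV(C) (Study Variables) lists eGFR, serum creatinine, "records of kidney disease events (such as renal function decline, initiation of dialysis, or kidney transplantation), and records of cardiovascular events". A separate line reads "Safety data: including all adverse events recorded". Section V (Descriptive statistical analysis) says "Primary and secondary outcome measures are descriptively analyzed (e.g., changes in renal function, incidence of cardiovascular events". None of these names all-cause death.

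On the source of data, section IV(D) says "The data will primarily be sourced from the hospital's electronic health record HIS system". It mentions no death register or other source for deaths outside the hospital. The background, just before section II, says the study is to cover patients with eGFR below 15, and the criteria in IV(B) set no eGFR limit. Entry starts on 15 December 2023; no end date or length of follow-up is given.

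**The concern.** A patient who dies cannot later start dialysis, receive a transplant or show further decline. Death is therefore a competing event for progression. When it is handled as ordinary censoring, Kaplan-Meier in effect assumes that the dead would have gone on to progress at the same rate as the survivors. One minus the curve then estimates risk in a setting where nobody dies, which is higher than the proportion of patients who actually progress.

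Deaths cannot be assumed to be rare in a cohort that reaches eGFR below 15. The curves are the part of the output that a clinician would read as the chance of progression, so their level matters. Because death is not a named variable, the data form may also lack what is needed to handle it properly. With no rule set in advance, the choice would be made after the data have been seen; section VIII reports that 43 cases already have preliminary results.

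**Working it through.** The documents give no progression rate, death rate, follow-up length or planned sample size, so there is no figure of the plan's own to reproduce. The check is an illustration, and every rate and horizon in it is an assumption.

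**Formulas.** Take constant cause-specific hazards per year, h_k for the kidney event and h_d for death, over T years.

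- One minus Kaplan-Meier, deaths censored: 1 − exp(−h_k·T)
- Cumulative incidence with death as a competing event (what Aalen-Johansen estimates): h_k/(h_k + h_d) × [1 − exp(−(h_k + h_d)·T)]

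**Worked case.** h_k = 0.15, h_d = 0.20, T = 2:

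- 1 − exp(−0.30) = 25.9%
- 0.15/0.35 × [1 − exp(−0.70)] = 0.4286 × 0.5034 = 21.6%
- Excess: 4.3 percentage points

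**Results for other values.**

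| h_k | h_d | T (years) | 1 − KM | Cumulative incidence | Excess (points) |
|---|---|---|---|---|---|
| 0.15 | 0.05 | 1 | 13.9% | 13.6% | 0.3 |
| 0.15 | 0.10 | 1 | 13.9% | 13.3% | 0.7 |
| 0.15 | 0.20 | 1 | 13.9% | 12.7% | 1.3 |
| 0.15 | 0.05 | 2 | 25.9% | 24.7% | 1.2 |
| 0.15 | 0.10 | 2 | 25.9% | 23.6% | 2.3 |
| 0.15 | 0.20 | 2 | 25.9% | 21.6% | 4.3 |
| 0.25 | 0.10 | 2 | 39.3% | 36.0% | 3.4 |
| 0.25 | 0.20 | 2 | 39.3% | 33.0% | 6.4 |

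The excess column is taken from unrounded values. Over a wider grid (h_k 0.05 to 0.20, h_d 0 to 0.20, T 0.5 to 3 years) the excess runs from 0 to 10.2 points. At 1 year it stays below 1 point for death hazards up to 0.10. With no deaths the two quantities are equal.

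**Effect on the group comparison.** The first formula contains no h_d. Under these assumptions, if deaths are known and censored, a difference in mortality between groups moves neither Kaplan-Meier curve. Log-rank and Cox then compare cause-specific hazards, which is a legitimate target.

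Masking arises in two other situations:

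- Deaths are not captured, and patients who died stay in the risk set as event-free up to the data cut.
- Crude event proportions are compared, as in the binary logistic regression of section V if it is applied to renal events (the plan's own example is cardiovascular events).

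Take equal kidney hazards of 0.15 and death hazards of 0.05 and 0.20. At 2 years the observed proportions would be 24.7% and 21.6%, an apparent renal advantage of about 3 points for the group with more deaths.

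**The case against.** Several points on the other side stand. Nothing in the plan says that deaths will be censored. That is the usual default when progression alone is the event, but no endpoint is defined, so a composite with death is not excluded. Kaplan-Meier is optional, conditional on follow-up being analysed, and offered for description. A reader might infer that the plan treats death as censoring and so overstates risk; the text supports this only conditionally.

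A reader might also infer that mortality will go unreported. The documents do not support that. All recorded adverse events are collected, cardiovascular events may include fatal ones, and the lists of kidney events and outcomes are given as examples. What is missing is an explicit all-cause death variable and a source for deaths outside the hospital.

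A third tempting reading is that Kaplan-Meier lets the group with more deaths appear to have fewer renal events. As shown above, that does not follow when deaths are known and censored.

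The size is also open to challenge. The 2-year horizon and the rates are assumptions, and the excess is small over short follow-up. For scale, with 43 patients (the cases organised so far, not a target) and complete follow-up, the 95% half-width around a 24% risk is about 1.96 × √(0.24 × 0.76/43) = 13 points, well above the 1.2 to 4.3 points at issue. Imprecision does not remove a bias of known direction, however, and the final cohort may be larger.

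**Conclusion.** The point holds in conditional form. The plan leaves the progression endpoint, the censoring rule and the handling of death undefined, and it does not name all-cause death. If progression alone is the event and deaths are censored, the Kaplan-Meier curves overstate absolute progression risk whenever deaths occur. With an assumed kidney hazard of 0.15 per year and death hazards of 0.05 to 0.20 per year, the excess is about 0.3 to 1.3 points at 1 year and 1.2 to 4.3 points at 2 years. Higher rates or longer follow-up make it larger. These sizes rest on constant hazards and on rates that the documents do not supply; the direction does not depend on the particular rates.

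The bias concerns absolute risk. Log-rank and Cox results stand as cause-specific comparisons if labelled so, and masking by death is limited to uncaptured deaths and crude proportions. The change should be made: a better-suited method is available at little cost.

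**What to change.** In IV(C), add date of death as recorded in the hospital system. State that patients whose vital status is unknown are censored at last contact, not carried event-free to the data cut.

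In V:

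- Define the progression endpoint, and replace its Kaplan-Meier curves with Aalen-Johansen cumulative incidence, with death as a competing event.
- Label the Cox model as cause-specific.
- Show deaths by group alongside the renal results.
- Add kidney event or death as a sensitivity analysis. Kaplan-Meier is suitable there, because death is then part of the event.

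The cost is one more item to extract and a little more output, using routines available in software the plan already names, such as R or Stata. Hospital records may miss deaths elsewhere. Such patients would be censored at last contact, so some upward bias would remain even in the Aalen-Johansen estimate, and the report should state this as a limitation. Tracing those deaths by contacting patients or families would bring in the consent requirements of IV(D) and VI, so the fix is confined to what the hospital system holds.
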